3.4.7 Physical Activity

We will assess exercise capacity using a 6-minute walking test (*6MWT*). The *6MWT* is a practical and simple test that has a negative correlation between total distance walked and length of hospital stay ($r = -0.62$) (70) and is suitable for use amongst patients with moderate-severe heart and lung disease. (71) Physical activity behavior will be measured using multi-directional accelerometers over a seven-day period, based on the methods described by Colley et al. (72) We have previously used these approaches to assess physical fitness and activity amongst cardiac patients.

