3.5.2 Safety and Baseline Assessments

A medical director, at each site, will oversee all cases and ensure patient eligibility and safety for program initiation and throughout program attendance for the study duration. All eligible and consented patients will be evaluated at baseline to ensure angina stability. Exercise prescription will be determined utilizing the standard practice of the Karvonen Equation adjusted according to pre-program exercise stress test. (21)Patients will also undergo a standard *6MWT* (73)(74)(75)(76)(77)(78) and will repeat the *6MWT* at the preoperative time point in both the control and *Prehab* groups to determine impact of the intervention. The *6MWT* was chosen because it requires minimal infrastructure and personnel to complete and has been demonstrated to be a valid prognostic tool for patient outcomes and is comparable to an exercise-stress test. (73)(75)(76)(77)This approach enables us to avoid potential scheduling issues that occur if a patient’s surgical date is moved up.

Patients who are deemed appropriate for enrolment into study will be randomized, following the completion of the baseline data collection, to one of two trial arms – control (standard of care (*StandC*) or treatment (*Prehab*). Baseline risk factor evaluation, anthropometrics, clinical markers, patient questionnaires (including frailty scores, cognitive assessment, and quality of life data) and physical activity data measured using accelerometers will be collected for all patients and repeated pre-operatively and at three-month follow up. Safety data including new hospitalization, worsening angina or heart failure and arrhythmias will be captured and all adverse events will be reportable to the study Data Safety Monitoring Board (*DSMB*). All patients in both groups will be referred to postoperative *CR* programming, as per local practice.

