5.1.1 Primary Outcome

Proportion of patients with hospital length of stay >7 days.

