5.2 Statistical/Analytical Plan

Objective 1: To determine if *Prehab* reduces the proportion of frail elderly patients requiring a prolonged hospital length of stay of >7 days. A univariable analysis will be undertaken to determine if hospital *LOS* > 7 days is associated with frailty and other patient-level factors. A stepwise multivariable logistic regression model will then be developed to determine if *Prehab* attendance is independently associated with a decreased risk of prolonged hospital length of stay > 7 days. As a secondary analysis, hospital *LOS* will also be compared as a continuous variable between the *Prehab* and standard care groups using a Mann-Whitney test.

“The PREHAB Study” (Pre-operative Rehabilitation for reduction of Hospitalization After coronary Bypass and valvular surgery.)

Objective 2: Does attending *Prehab* influence frailty, exercise capacity, physical activity behavior, in-hospital complications, and *HRQoL*? Although we will employ four different measures of frailty, based on our preliminary data and based on a Task Force’s position statement(90), the Modified Fried Criteria will be the primary frailty outcome over time from baseline to the end of *Prehab* program (pre-operatively), or from baseline to the 3-month post-operative follow-up. The primary measure of exercise capacity will be the *6MWT* and will be analysed with univariable linear regression models to evaluate the association between the *6MWT* and *Prehab* attendance. Accelerometers will be used to objectively measure the number of minutes spent performing moderate to vigorous physical activity (*MVPA*) and total physical activity (*TPA*) per day for a period of 7 days and compared between groups. A composite outcome for a major adverse cardiac event (i.e. *MACCE* = in-hospital stroke, myocardial infarction, renal failure requiring dialysis and death) and delirium will be compared between groups using a Chi-Square or Fisher’s Exact test. A multivariable logistic regression will be used to identify if *Prehab* is independently associated with in-hospital delirium. The *SF-12v2* and *EQ-5D* scores, after normative standardization, will be analyzed through use of a repeated *ANOVA* to allow for a standardized group and group/time interaction effect estimation.

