5.3 Sample Size Calculation

The sample size calculation was based on the primary objective – determining the effect of *Prehab* on rates of prolonged hospital length of stay > 7 days. Our preliminary data, demonstrated the proportion of frail patients in the Control group with a hospital length of stay > 7 days to be 58.3%. For the *Prehab* group, based on improvements in functional capacity in our pilot *RCT* and the work by Arthur et al14, we believe an absolute 20% reduction in proportion of patients that require prolonged hospital length of stay of greater than 7 days, is feasible. A sample size of 194 individuals (97 in each group) will be required for a two-tailed test at an alpha of 0.05 and power of 80%. All patients assigned to the pilot *Prehab* group completed the intervention, however, we are mindful that we will be recruiting frail, elderly patients who may have a higher dropout rate. Hence, we are estimating a 20% dropout rate and plan to recruit 244 individuals (122 in each study arm) to achieve an eventual sample size of 194 after dropout.

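### Baseline 6-minute walk distance is collected in both arms and cited as correlated with hospital stay, but section 5.2 commits no length-of-stay analysis to adjusting for it; fixing it in the model would secure precision worth about 0 to 9 points of power over an unadjusted analysis

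*Combined protocol and SAP*

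**What the plan says.** The primary outcome in section 5.1.1 is binary: "Proportion of patients with hospital length of stay >7 days". Section 5.2, Objective 1, first screens frailty and further patient-level variables, which it does not list, one at a time. Then: "A stepwise multivariable logistic regression model will then be developed to determine if" Prehab attendance is independently associated with a lower risk. No entry or removal threshold is given, and no covariate is named as always kept. As a secondary analysis, length of stay is compared between the Prehab and "standard care groups using a Mann-Whitney test". The 6-minute walk test (6MWT) appears in section 5.2 only under Objective 2, as the measure of exercise capacity.

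Elsewhere the protocol ties the 6MWT to length of stay. Section 3.4.7 justifies it by a "negative correlation between total distance walked and length of hospital stay", with r = -0.62. Section 3.5.2 has patients walk at the baseline assessment and again "at the preoperative time point in both the control and" Prehab groups. The same section says suitable patients are "randomized, following the completion of the baseline data collection".

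The sample size in section 5.3 is a plain two-proportion calculation with no covariate adjustment.

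**The concern.** A baseline variable that predicts the outcome can sharpen the treatment comparison at almost no cost, provided it is measured before randomization and fixed in the model beforehand. The protocol appears to have such a variable and gives its own reason to expect it to predict hospital stay. No length-of-stay analysis is committed to using it.

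Three things are left open:

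- Whether the baseline walk enters the primary model at all depends on an unlisted candidate set and on selection in the trial data.
- The loose description of the candidates does not bar the pre-operative walk. That walk is measured after randomization and is something Prehab is meant to change, so adjusting for it could remove part of the effect under test.
- The Mann-Whitney comparison of length of stay has no place for a covariate.

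At stake is some precision on the primary outcome, and a primary analysis whose content is settled in advance.

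**Working it through.** **1. The plan's own figure.** Inputs from section 5.3: "the proportion of frail patients in the Control group with a hospital length of stay > 7 days to be 58.3" per cent; an "absolute 20% reduction in proportion of patients", giving 38.3%; two-sided alpha 0.05; power 80%. The pooled formula is

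n = [1.960·√(2·p̄·q̄) + 0.8416·√(p1·q1 + p2·q2)]² / (p1 − p2)².

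With p̄ = 0.483: √0.4994 = 0.7067 and √(0.2431 + 0.2363) = 0.6924. So n = (1.3851 + 0.5827)² / 0.04 = 96.8, that is 97 per arm. Power at 97 per arm is 80.1%. Allowing for 20% dropout, 97 / 0.8 = 121.25, so 122 per arm and 244 in all. The stated figures reproduce without any covariate.

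**2. Value of adjustment against an unadjusted model.** I simulated trials with 97 per arm. A normal variable underlying length of stay was correlated |r| with baseline walk distance and cut so that the marginal rates stayed at 58.3% and 38.3%. The Wald test for arm was taken from a logistic model with and without baseline walk distance. There were two runs, of 6,000 and 20,000 trials per setting. The Monte Carlo standard error of a power near 80% is √(0.8·0.2/6000) = 0.5 points and √(0.8·0.2/20000) = 0.3 points respectively.

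| Assumed \|r\| | Unadjusted → adjusted, 6,000 trials | Unadjusted → adjusted, 20,000 trials | Gain (points) |
|---|---|---|---|
| 0.62 | 80.6% → 89.3% | 79.8% → 89.4% | about 9 |
| 0.5 (0.495 in the second run) | 80.4% → 85.9% | 80.6% → 86.0% | 5 to 6 |
| 0.4 | 81.2% → 84.5% | 80.4% → 83.6% | about 3 |
| 0.3 | 80.9% → 82.6% | 80.1% → 81.8% | about 2 |
| 0.2 | 80.6% → 80.6% | 81.2% → 81.5% | about 0 |

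With |r| = 0.62 in controls and 0.3 in the Prehab arm the gain is 4.5 points (80.5% → 85.0%). With no treatment effect, type I error of the adjusted test is 5.0%.

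**3. Cross-check at 0.62.** Cutting the outcome in two weakens the correlation to 0.62 × 0.798 = 0.49. The residual variance is then 1 − 0.49² = 0.76, equivalent to 97 / 0.76 = 128 per arm. The formula in step 1 gives 89.7% power at that size, in line with the simulation.

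**4. Value of fixing the covariate, if it would otherwise be screened.** A further simulation (4,000 trials per setting) offered baseline walk distance as a single candidate, kept if p < 0.05, with arm always in the model.

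| Assumed \|r\| | Forced in | Screened |
|---|---|---|
| 0.62 | 89.6% | 89.6% |
| 0.5 | 86.6% | 86.6% |
| 0.4 | 83.9% | 83.8% |
| 0.3 | 82.2% | 82.1% |
| 0.2 | 80.6% | 80.3% |

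In the 20,000-trial run the covariate was significant in essentially all trials at 0.62 and 0.495, 99.5% at 0.4, 92% at 0.3 and 59% at 0.2. This does not imitate a full stepwise search over many candidates.

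**5. Length of stay as a continuous outcome.** In a linear model, r = 0.62 would cut residual variance by 0.62² = 38%. That is only indicative. Length of stay is skewed (median 8 days, interquartile range 6 to 12, in the frail patients of section 3.1.1.1), and no gain was computed for an ordinal model.

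**The case against.** The strongest reply is that an unadjusted model is not the planned primary analysis. Section 5.2 plans a multivariable model, baseline walk distance is a patient-level variable, and nothing excludes it. Step 4 supports this: when the walk matters it is selected, and when it is missed there is little to gain. A reader might infer that the plan forfeits 8 or 9 points of power. The documents do not support that. It would need the walk never to be offered to the model, which section 5.2 neither says nor rules out.

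The cited correlation is also one sentence resting on one outside study. Section 3.4.7 does not give the timing of that walk, the number of patients or the type of correlation. Here entry is limited to Clinical Frailty Scores from 3 to below 7. The wait before surgery varies (median 12 weeks in Manitoba, section 3.5.6), and Prehab aims to change walking distance in one arm. Each could weaken the relation, so 0.62 is better read as the top of a range.

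Nor should the walk be called the strongest predictor on the strength of Table 6. Fried status (37.7% against 58.3%) explains about 4% of the variance of the binary outcome, but setting that beside 0.62² compares different scales. On a latent-normal scale the Fried correlation is about 0.32, or roughly 10%.

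Finally, the baseline list in section 3.5.2 does not repeat the 6MWT, and section 3.5.5.4.2 pairs it with the Prehab stress test. A pre-randomization walk in every patient is the natural reading, since a repeat in both arms implies a first walk in both, but it is not stated outright.

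All of this stands. It limits the size of the point, but the covariate set remains unspecified, the post-randomization walk is not excluded, and the Mann-Whitney test is unadjusted.

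**Conclusion.** The point holds as a low-cost improvement. It is not an error in the design. Section 5.2 does not commit any length-of-stay analysis to a baseline covariate that the protocol itself links to hospital stay.

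Relative to an unadjusted analysis with 97 per arm, adjustment is worth about 0 to 9 points of power for |r| from 0.2 to 0.62. This assumes a normal variable underlying length of stay and, except for the 4.5-point case, the same correlation in both arms. Relative to a model that screens the baseline walk as a candidate, fixing it adds at most about 0.3 points in the settings simulated. For the primary outcome, then, the benefit lies in making the gain certain, removing data-driven selection and keeping the pre-operative walk out.

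A reader might conclude that the trial is underpowered or that its primary conclusion turns on this choice. Neither follows: the planned 80% is reached without adjustment.

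**What to change.** In section 5.2, Objective 1:

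- State that the primary logistic model of stay beyond 7 days contains assigned arm and baseline (pre-randomization) 6MWT distance as a fixed continuous covariate, not subject to selection.
- State that the pre-operative 6MWT is not used as a covariate in any length-of-stay analysis.
- Report the adjusted risk difference by standardization, so that it is on the same scale as the 20-point difference in section 5.3.
- Add a covariate-adjusted analysis of length of stay, for example a proportional-odds model on arm and baseline 6MWT, alongside the Mann-Whitney test.
- Give a simple rule for a missing baseline walk, for example the overall mean with a missingness indicator, so that no randomized patient is dropped. Section 6.3 refers missing data to the statistical analysis plan, and section 5.2 gives no rule.

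In section 3.5.2, say outright that every patient completes the 6MWT before randomization.

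The cost is SAP and protocol wording and one degree of freedom for the continuous covariate, or one more if a missingness indicator is needed. On the natural reading of section 3.5.2 the data are already being collected. If the correlation proves weak, little is lost: at |r| = 0.2 adjusted and unadjusted power were the same to within 0.3 points.

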5.1.2 Secondary Outcomes

(1) pre-operative frailty, (2) exercise capacity, (3) physical activity behavior, (4) in-hospital outcomes, (5) 1-year clinical outcomes, (6) 1-year health-related quality of life, (7) cost-analysis.

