To address patient safety, all Prehab participants underwent a standardized exercise stress test prior to the initiation of the Prehab program.⁹ Additionally, during the Prehab program, trained medical staff, including a cardiologist, nurses, and an exercise specialist monitored the participants. Data related to Prehab safety outcomes were collected from patient charts at the medical fitness facility after patients had completed the Prehab program and included fatal or non-fatal myocardial infarctions, exercise-induced arrhythmias, unstable angina, and hospitalization owing to Prehab participation. In addition, data on operative and postoperative complications were collected from hospital chart reviews and included 30-day mortality, atelectasis, atrial fibrillation, stroke, renal failure requiring dialysis, prolonged ventilation, sternal wound infection, reoperation, and re-hospitalization.

The primary study outcome was a change in walking distance assessed using the 6-minute walk test (6MWT), based on standardized guidelines.¹⁰ The 6MWT correlates with physical fitness as assessed by a maximal graded exercise test.¹¹ In accordance with standardized guidelines, gait speed was measured using a 5-m gait speed test, a predictor of mortality and morbidity in patients undergoing cardiac surgery.¹²

Physical activity was objectively measured using an actical accelerometer (Phillips-Respironics¹³). Accelerometer data were analyzed utilizing the protocol described by Colley et al.¹³ Specifically, physical activity intensity was measured in counts/min (light activity = 100–750 counts/min; moderate to vigorous physical activity (MVPA) ≥750 counts/min), which was subsequently analyzed in minutes/week. Participants wore an accelerometer during their waking hours for seven-day periods. A valid day of accelerometer data was defined as >10 hours of wear time. Accelerometer data were analyzed in ≥10-minute intervals (i.e. MVPA_{10min}, TotalPA_{10min}), as well as sporadically in bouts of ≥30 seconds (i.e. MVPA_{spor}, TotalPA_{spor}). Physical activity accumulated in 10-minute bouts or more is currently recommended by the *Canadian Physical Activity Guidelines* for health benefits.¹⁴ We chose to analyze physical

activity in sporadic bouts owing to emerging evidence suggesting that even very short activity bouts are associated with health physical fitness.¹⁵

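### Minor, secondary outcome: the 6MWT regression in section 5.2 names no response and no baseline covariate; adjusting for baseline by assigned arm gains precision at almost no cost

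*Combined protocol and SAP*

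**What the plan says.** Section 5.2, Objective 2, states: "The primary measure of exercise capacity will be the *6MWT* and will be analysed with univariable linear regression models". The stated purpose is "to evaluate the association between the *6MWT* and *Prehab* attendance". Elsewhere in section 5.2 the plan writes multivariable where covariates are intended (prolonged stay, delirium), so univariable can be taken at its word. The time point and form of the response are not given.

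Section 3.5.2 says that patients "will repeat the *6MWT* at the preoperative time point in both the control and *Prehab* groups to determine impact of the intervention". It places randomization "following the completion of the baseline data collection", so the baseline walk precedes allocation. The same Objective 2 paragraph follows frailty from baseline and gives quality of life a repeated-measures ANOVA "to allow for a standardized group and group/time interaction effect estimation". Section 3.2 commits the trial to intention-to-treat analysis.

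**The concern.** Baseline is used for two neighbouring outcomes but is not mentioned for the 6MWT, although it is measured in every randomized patient. Two readings of section 5.2 are open:

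- a regression of the pre-operative value, which ignores baseline;
- a regression of the change from baseline, which is plausible because change in walking distance was the pilot's primary outcome.

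With randomized arms neither reading is biased, but each can waste information, and leaving the choice open allows it to be made after the data are seen. Attendance is also a post-randomization variable. Taken literally, a regression on it is not the randomized comparison that section 3.2 promises.

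**Working it through.** The documents give no power or detectable difference for the 6MWT, so there is no planned figure to reproduce. The planned 97 and 122 per arm (section 5.3) were set for length of stay and are used here only as sample sizes.

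**Inputs.** Table 2 of the pilot manuscript, mean ± SD in metres:

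| Arm | n | Baseline | Pre-operative |
|---|---|---|---|
| Standard care | 7 | 337 ± 52 | 332 ± 27 |
| Prehab | 8 | 342 ± 79 | 474 ± 101 |

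The between-arm difference in change is printed as 136 (61 to 209).

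**Step 1: SDs and correlation.**
- Baseline: √[(6·52² + 7·79²)/13] = 67.9 m.
- Pre-operative: √[(6·27² + 7·101²)/13] = 76.3 m.
- Change: half-width (209 − 61)/2 = 74; SE = 74/2.160 (t, 13 df) = 34.3; SD = 34.3/√(1/7 + 1/8) = 66.2 m.
- r = (67.9² + 76.3² − 66.2²)/(2·67.9·76.3) = 0.58, so r² = 0.34. The Fisher interval with n = 15 is about 0.10 to 0.84.
- If the printed interval used z = 1.96 instead, the SD of change is about 73 m and r = 0.49.

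**Step 2: residual variance with the covariate.** Adjusted SD = 76.3·√(1 − 0.34) = 62.0 m.
- Against the value, the cut is r² = 34%, worth about 1/(1 − 0.34) = 1.5 times the sample size.
- Against the change, the cut is 1 − 62.0²/66.2² = 12%. It would be 21% if baseline and pre-operative SDs were equal.
- With r = 0.49 the cuts are 24% and 17%.

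**Step 3: difference detectable with 80% power,** 2.80·SD·√(2/n):

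| n per arm | Value | Change | Adjusted |
|---|---|---|---|
| 97 | 30.7 m | 26.6 m | 24.9 m |
| 122 | 27.4 m | 23.7 m | 22.2 m |

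**Step 4: power at 97 per arm** (noncentral t, two-sided 0.05):

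| True difference | Value | Change | Adjusted |
|---|---|---|---|
| 25 m | 62% | 74% | 80% |
| 30 m | 78% | 88% | 92% |
| 40 m | 95% | 99% | 99% |
| 50 m | 99.5% | >99.9% | >99.9% |

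The documents name no expected or important 6MWT difference, so these effects are illustrations.

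**Step 5: dependence on r.** Write sb and sp for the baseline and pre-operative SDs. The cut against the value is r². The cut against the change is 1 − sp²(1 − r²)/(sb² + sp² − 2·r·sb·sp). Over r = 0.10 to 0.84 the first runs from 1% to 71%. The second runs from 39% to 1% with pilot SDs, or 45% to 8% with equal SDs. They cross at r = sb/(2·sp): 0.445 with pilot SDs, where both are 20%, and 0.50 with equal SDs, where both are 25%. At any r, the less favourable reading therefore gives up at least 20% (pilot SDs) or 25% (equal SDs) of the variance.

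**The case against.** The strongest reply is that this is largely a preference. If the sponsor meant change from baseline, baseline is already used, and at r = 0.58 the covariate improves the detectable difference only from 26.6 to 24.9 m, or 1.7 m. An effect near the pilot's 136 m would be found by any model. Both points are right, and they are why the matter is minor. They do not supply the missing definition of the response.

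On the inputs, r comes from 15 patients having bypass surgery only, with pre-operative SDs of 27 and 101 m (variance ratio about 14). A pooled r is rough. The post-operative interval in the same table (62 to 209) is centred on 135.5, not on its stated 123, so it was not used. These are reasons to rely on Step 5 more than on the point value.

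The 97 per arm is the length-of-stay target. Short notice of surgery defeated pre-operative accelerometry in the pilot: 11 of 15 patients were operated on within 1–3 days of notice. Some pre-operative walks may be lost too, so the powers are best cases. All three models need the pre-operative walk, so their ranking is unchanged.

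Section 3.5.5.4.2 pairs the 6MWT with the stress test, which section 3.5.5 places in the Prehab group's intake. However, section 3.5.2 puts completion of baseline data before randomization for both arms.

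Two remaining points are fair. A sentence about the pre-operative visit alone would leave any later walk without an analysis (section 9.2 mentions a 1-year exercise test). The word attendance also appears in Objective 1, so it is not peculiar to this outcome.

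**Conclusion.** The concern holds, as a minor one. Section 5.2 leaves the 6MWT response undefined and omits an available pre-randomization covariate. By assigned arm, the remedy is a gain in precision, not a correction of bias. Its size is about 34% of residual variance against the pre-operative value and about 12% against change, assuming the pilot's SDs and r of about 0.58. Apart from one degree of freedom, the covariate model is at least as precise as either reading whatever r is. The more favourable reading may lose almost nothing. The choice affects power materially only for true differences of roughly 30 m or less. The primary outcome and sample size are unaffected.

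**What to change.** In section 5.2, replace the 6MWT sentence with wording to this effect: *Pre-operative 6MWT will be analysed by linear regression on assigned arm (intention to treat, not attendance), with baseline 6MWT as a covariate.* If a later 6MWT is also to be analysed, state that the same model applies with that visit as the response.

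The cost is SAP wording and one model degree of freedom, with no new data or visit. A patient without a baseline 6MWT would drop out of the adjusted model; this should be rare, because randomization follows completion of baseline data collection.
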